8.0 DOSE MODIFICATIONS

8.1 NCI Common Terminology Criteria for Adverse Events

This study will utilize the CTCAE (NCI Common Terminology Criteria for Adverse Events) Version 4.0 for toxicity and Serious Adverse Event reporting. A copy of the CTCAE Version 4.0 can be downloaded from the CTEP home page (<http://ctep.cancer.gov>). All appropriate treatment areas should have access to a copy of the CTCAE Version 4.0.

8.2 Dose Modifications

There are no dosage modifications for this study.

8.4 Adverse Event Reporting

Toxicities (including suspected reactions) that meet the expedited reporting criteria as outlined in [Section 16.0](#) of the protocol must be reported to the Operations Office, Study Chair, the NCI via CTEP-AERS, and to the IRB per local IRB requirements.

9.0 STUDY CALENDAR

REQUIRED STUDIES	PRE STUD Y	Hospitalization		Year 1				Year 2				Year 3				Year 4	Year 5	Year 6
		Day of Surgery	Day of Discharge	Mo	Mo	Mo	Mo	Mo	Mo	Mo	Mo	Mo	Mo	Mo	Mo	Mo	Mo	Mo
				3	6	9	12	15	18	21	24	27	30	33	36	48	60	72
PHYSICAL																		
History and Physical Exam	X ^a			X	X	X	X		X		X		X		X	X	X	X
Height, Weight and Performance Status	X																	
Hospitalization assessment ^b			X															
Adverse Event/Morbidity assessment ^c				X	X													
LABORATORY																		
Bilirubin	X			X	X	X	X		X		X		X		X	X	X	X
SGOT and SGPT	X			X	X	X	X		X		X		X		X	X	X	X
Alkaline Phosphatase ^d	X			X	X	X	X		X		X		X		X	X	X	X
STAGING																		
TURBT	X																	
Bimanual Exam	X																	
X-RAYS AND SCANS																		
CT or MRI of abdomen and pelvis	X				X		X		X		X		X		X	X	X	X
2 view Chest X-ray or CT of the Chest	X			X	X	X	X		X		X		X		X	X	X	X
Bone Scan, PET/CT or other imaging directed at potential visceral or node metastatic sites	X ^d																	
SPECIMEN SUBMISSION																		
Two Paraffin Embedded Blocks or 10 unstained slides from Primary Tumor		X ^e																
8 unstained, formalin-fixed paraffin embedded (FFPE) sections from the left-pelvic and right-pelvic lymph nodes		X ^e																

Calendar continued on next page. Click here for [footnotes](#).

TREATMENT (see Section 7.0 for details)														
Surgical assessment of nodal dissection ^f		X												
Standard or Extended Pelvic Lymph Node Dissection		X												
Submission of Materials for Surgical Review ^g		X												
Adjuvant chemotherapy ^h				X										

NOTE: Forms are found on the protocol abstract page of the SWOG website (www.swog.org). Forms submission guidelines are found in [Section 14.0](#).

- a Physical exam and medical history must be completed within 28 days prior to registration (see [Section 5.3b](#)).
- b See [S1011](#) Surgeons Post-Op Data Form (see protocol abstract page, www.swog.org).
- c Morbidity data **collected** on both [S1011](#) Surgeon's Post-Op Data Form Standard Versus Extended LND and [S1011](#) Surgeon's 90-Day Assessment Form Standard Versus Extended IND (see protocol abstract page, www.swog.org).
- d Bone scan required if patient has an elevated alkaline phosphatase or bone pain.
- e For patients who consent to specimen banking, specimens must be collected after completion of the final pathologic evaluation.
- f See [S1011](#) Intra-Op Surgical Assessment Form (see protocol abstract page, www.swog.org).
- g See [Section 12.2](#)
- h For patients who did not receive neoadjuvant chemotherapy, post operative adjuvant chemotherapy for pTany, N+ or pT3-4, N0 is strongly recommended, but not required and will be left up to the treating physician.

10.0 CRITERIA FOR EVALUATION AND ENDPOINT DEFINITIONS

10.1 Measurability of lesions

- a. **Measurable disease:** Measurable disease is defined differently for lymph nodes compared with other disease and will be addressed in a separate section below.
 1. Lesions that can be accurately measured in at least one dimension (longest diameter to be recorded) as ≥ 2.0 cm by chest x-ray, by ≥ 1.0 cm with CT or MRI scans, or ≥ 1.0 cm with calipers by clinical exam. All tumor measurements must be recorded in decimal fractions of centimeters (or millimeters).

The defined measurability of lesions on CT scan is based on the assumption that CT slice thickness is 0.5 cm or less. If CT scans have slice thickness greater than 0.5 cm, the minimum size for a measurable lesion should be twice the slice thickness.
 2. **Malignant lymph nodes** are to be considered pathologically enlarged and measurable if it measures ≥ 1.5 cm in **SHORT AXIS** (greatest diameter perpendicular to the long axis of the lymph node) when assessed by scan (CT scan slice recommended being no greater than 0.5 cm).
- b. **Non-measurable disease:** All other lesions (or sites of disease), including small lesions (longest diameter < 1.0 cm or pathologic lymph nodes with ≥ 1.0 cm to < 1.5 cm short axis), are considered non-measurable disease. Bone lesions, leptomeningeal disease, ascites, pleural/pericardial effusions, lymphangitis cutis/pulmonitis, inflammatory breast disease, and abdominal masses (not followed by CT or MRI), are considered non-measurable as are previously radiated lesions that have not progressed.
- c. **Notes on measurability**
 1. For CT and MRIs, the same type of scanner should be used and the image acquisition protocol should be followed as closely as possible to prior scans. Body scans should be performed with breath-hold scanning techniques, if possible.
 2. PET-CT: At present, the low dose or attenuation correction CT portion of a PET-CT is not always of optimal diagnostic CT quality for use with RECIST measurements. However, if the site can document that the CT performed as part of a PET-CT is of identical diagnostic quality to a diagnostic CT, then the CT portion of the PET-CT can be used for RECIST measurements and can be used interchangeably with conventional CT.
 3. Ultrasound: Ultrasound is not useful in assessment of lesion size and should not be used as a method of measurement.
 4. Cystic lesions that meet the criteria for radiographically defined simple cysts should not be considered as malignant lesions (neither measurable nor non-measurable) since they are, by definition simple cysts.
 4. If a target lesion becomes very small some radiologists indicate that it is too small to measure. If the lesion is actually still present, a default measurement of 0.5 cm should be applied. If the radiologist believes the lesion has gone, a default measurement of 0.0cm should be recorded.

10.2 Recurrence

Criteria for recurrence will include measurable disease on cross-sectional imaging or plane radiography targeting lung, liver and bone as most common sites for recurrence. Bone scintigraphy may be used according to Good Medical Practice. Local pelvic recurrence may be determined by cross-sectional imaging and/or DRE (and confirmed by biopsy if indicated). PET/CT may be used to confirm suspicious abnormalities on other imaging modalities.

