7.7 Follow-Up Period

All patients will be followed for recurrence and survival for a maximum of 6 years after Step 2, Randomization or until death (whichever occurs first).

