10.3 Disease-Free Survival

From date of randomization to date of first documentation of relapse/recurrence or death due to any cause. Patients last known to be alive without report of relapse/recurrence are censored at date of last contact.

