11.0 STATISTICAL CONSIDERATIONS

11.1 Accrual Goal

We anticipate that 113 eligible patients will be randomized per year to this study on a group-wide basis. We will also assume that 10 percent of enrolled patients will be found to be clinically or pathologically ineligible and hence, not randomized so our Step 1 sample size will be inflated to account for this. Based on an extensive review of the contemporary literature (see [Section 2.0, Table 1](#)), we estimate that 3-year disease free survival (DFS) for patients at increased risk for pelvic and iliac node metastasis undergoing a standard pelvic lymphadenectomy is 55%. A poll of centers of excellence suggest that a 10-12% improvement in 3-year DFS (65-67%) for patients in extended lymphadenectomy would be meaningful and establish extended node dissection as the standard of care in this patient population. Assuming exponential survival, 5 years of patient accrual, 3 additional years of follow-up and a sample size of 564 eligible patients (282 per arm), the study has 85% power to detect a 28% reduction in the hazard rate of progression or death with extended lymph node dissection compared to limited

dissection (hazard ratio 0.72). This corresponds to an improvement in 3-year DFS from 55% to 65% or alternatively median DFS would be extended from 3.5 to 4.8 years if the DFS distributions are exponential. We will use a one sided stratified log rank test with $\alpha = 0.025$, and the analysis will be intent-to-treat.

Assuming an ineligibility rate of 10%, total accrual (eligible + ineligible patients) to the initial step is expected to be 620 patients.

As a secondary endpoint, overall survival is also of great interest. If extended lymph node dissection is found to be statistically significantly better than standard lymph node dissection with respect to DFS, then an analysis of the survival endpoint will follow. We will allow for three more years of follow-up after the primary analysis has been conducted to assess potential survival differences. If we assume that the standard arm has 5-year survival of 55% then we will have 83% statistical power to detect a hazard ratio of 0.72 (55% vs. 65% survival at 5 years) using a one-sided stratified logrank test with alpha=0.025.

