12.2 Surgery Review

- a. All surgeries performed as part of this study will undergo a central surgical review. The goal of this review is to verify that the lymph node dissection was done according to the assigned randomization and the criteria specified in Section 7.0 of the protocol.
- b. The following are required to be submitted within 14 days of surgery to the SWOG Data Operations Center in Seattle (see [Section 14.4b](#)):
 1. **S1011** Intra-Op Surgical Assessment Form Standard versus Extended LND;
 2. Digital image(s) of intra-operative photo(s) showing extent of node dissection;
 3. Copy of the operative report(s);

4. Copy of corresponding pathology report(s).

The **S1011** Urology Study Chairs will review all these data within 7 days of receipt and interact with the surgeons at each site to provide feedback in order to ensure the consistency of the extent of node dissection in the two arms.

Independent oversight will be provided by the SWOG Surgery Quality Committee who will review these data at least annually and make recommendations for improvement in monitoring and data collection as needed.

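### Does calling bone lesions non-measurable in Section 10.1 keep a bone-only relapse out of disease-free survival under Section 10.2?

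*Combined protocol and SAP*

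**What the plan says.** Section 10.2 (Recurrence) gives the imaging criterion: "Criteria for recurrence will include measurable disease on cross-sectional imaging or plane radiography targeting lung, liver and bone as most common sites for recurrence". It then adds other routes. For bone scans, "Bone scintigraphy may be used according to Good Medical Practice". Local pelvic recurrence may be found by cross-sectional imaging or rectal examination, with biopsy if indicated. For PET, "PET/CT may be used to confirm suspicious abnormalities on other imaging modalities".

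Section 10.1b (Measurability of lesions) says that "Bone lesions, leptomeningeal disease, ascites, pleural/pericardial effusions, lymphangitis cutis/pulmonitis, inflammatory breast disease, and abdominal masses (not followed by CT or MRI), are considered non-measurable". It makes no exception for bone lesions by size or soft-tissue component.

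Section 10.3 defines DFS as running "From date of randomization to date of first documentation of relapse/recurrence or death due to any cause". Under Section 7.7 patients are "followed for recurrence and survival for a maximum of 6 years after Step 2, Randomization" or until death.

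In the study calendar (Section 9.0), footnote d requires a bone scan when alkaline phosphatase is raised or there is bone pain. The footnote is attached to two rows: the additional-imaging row, marked pre-study only, and the alkaline phosphatase row, marked at follow-up visits to month 72.

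The only central review described is in Section 12.2: "All surgeries performed as part of this study will undergo a central surgical review". Its stated goal is to verify the node dissection.

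**The concern.** DFS is the primary endpoint, and control-arm DFS events trigger the three interim analyses and the final one. Section 10.2 names bone as one of three common relapse sites, while Section 10.1b puts every bone lesion outside measurable disease. Taken at face value, the bone part of the criterion can never be satisfied.

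Two careful sites could therefore date the same patient differently. One would report relapse at the first positive bone image. The other would wait until measurable disease appeared elsewhere or the patient died. The operating surgeon knows the assigned arm, no blinded or central assessment of recurrence is described, and no sentence says outright that a positive bone finding is a relapse. If event dates depended on how each site read the text, the DFS curves and the timing of the analyses would depend on it too.

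**Working it through.** **1. The text**

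- The verb in the Section 10.2 criterion is *include*. Measurable disease is one way to establish recurrence, and nothing says that it is the only way.
- The same sentence puts bone among the most common recurrence sites, and the next sentence permits bone scintigraphy. To leave bone disease out, a site would have to conclude that a named common site of recurrence can never be a recurrence.
- Section 10.3 asks for first documentation of relapse and does not mention measurability. Death from any cause is also an event, so even the strictest reading usually postpones a bone-only relapse rather than losing it.
- Footnote d, on the alkaline phosphatase row, can be read as triggering bone scans during follow-up. Its reach is ambiguous, and it does not say that a positive scan counts. It fits a plan in which bone relapse is looked for.
- Section 10.1 is general lesion-measurement language. It mentions inflammatory breast disease and target lesions, which have little place in a trial of patients rendered disease-free by surgery.

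**2. The design figures, reproduced**

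Inputs from Sections 11.1 and 11.2: control 3-year DFS 55%, hazard ratio 0.72, 282 patients per arm, 5 years of accrual (taken as uniform), 3 further years, one-sided alpha 0.025, and 184 control events at the final analysis.

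- Control hazard: λ0 = −ln(0.55)/3 = 0.1993 per year. Extended: λ1 = 0.72 × 0.1993 = 0.1435 per year.
- Expected events per arm: 282 × [1 − (e^(−3λ) − e^(−8λ))/(5λ)].
- Control: 282 × [1 − (0.5500 − 0.2031)/0.9964] = 183.8, against 184 stated. Extended: 151.1. Total: 335.0.
- Power: Φ(|ln 0.72| × √335.0/2 − 1.960) = Φ(1.046) = 85.2%, against 85% stated.

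The design figures stand, and this point disputes none of them.

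**3. What late counting would do**

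The documents give neither the share of bone-only relapses nor the gap to other disease or death. Assume that a share *s* of DFS events is bone-only and is counted *g* years late, at every site and in both arms.

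- Control 3-year DFS = 1 − [(1 − s)(1 − e^(−3λ0)) + s(1 − e^(−λ0(3 − g)))]. For s = 10%, g = 2: 1 − [0.9 × 0.45 + 0.1 × 0.1807] = 57.7%.
- The hazard ratio is the large-sample Cox value at year 8 with the 6-year follow-up limit, found numerically.
- The trigger date is the time from the start of accrual at which expected control events reach 184.

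| s | g (years) | Control 3-year DFS | Hazard ratio | 184 control events, 6-year limit (years) | Same, no limit (years) |
|---|---|---|---|---|---|
| 0 | – | 55.0% | 0.720 | 8.49 | 8.01 |
| 5% | 0.5 | 55.3% | 0.720 | 8.54 | 8.04 |
| 5% | 1 | 55.6% | 0.720 | 8.59 | 8.06 |
| 5% | 2 | 56.3% | 0.721 | 8.72 | 8.13 |
| 10% | 0.5 | 55.6% | 0.720 | 8.59 | 8.06 |
| 10% | 1 | 56.2% | 0.721 | 8.70 | 8.12 |
| 10% | 2 | 57.7% | 0.722 | 8.96 | 8.25 |

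With the limit, the delay runs from (8.541 − 8.494) × 12 = 0.6 months to (8.962 − 8.494) × 12 = 5.6 months. Without it, the delay runs from (8.036 − 8.010) × 12 = 0.3 to (8.250 − 8.010) × 12 = 2.9 months.

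**4. Why both arms is the relevant case**

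Patients are randomized individually, during surgery (Section 7.1). A site's reading of Section 10.2 therefore applies to its patients in both arms. Site is not a stratification factor (Section 6.0), so balance within a site is left to chance, which adds noise but no direction. If only some sites read the text strictly, the effective share falls below *s* and the effect is smaller than in the table.

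**The case for a change.** The strongest case for a change is that the two sections do conflict and nothing in the text formally settles the conflict. Permission to use scintigraphy does not say that a positive scan is a relapse. First documentation presupposes a definition of recurrence, which is the part left loose. Assessment is not described as blinded or centrally reviewed, and a clarifying sentence would cost almost nothing.

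The wording mismatch stands, and so does the absence of an explicit statement. The consequence is much weaker. Late counting requires treating a non-exclusive list as exclusive, against the sentence that names bone as a common recurrence site. A material shift in the hazard ratio would need the reading to differ by arm rather than by site, and no passage suggests that. Unblinded reporting applies to every relapse site and is not created by the measurability wording.

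A remedy that dated every relapse at the first image showing it would raise a new question. Section 10.2 provides for confirmation by PET/CT or biopsy, and such a rule leaves open which date an equivocal, later-confirmed lesion should take. Relapse is reported on the Follow Up Form (Section 14.4), which is not reproduced in the documents, so how it records site and date cannot be judged here.

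**Conclusion.** Sections 10.1b and 10.2 are loosely worded together, but the plan does not exclude bone-only relapse from DFS, and sites and analysts would sensibly count it. A sentence saying so would only record the evident intent. No bias, wrong design figure or change to the analysis follows.

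On the assumed 5-10% share and 6-24 month gap, with both arms read alike, the hazard ratio moves from 0.720 to at most 0.722. Control 3-year DFS would read at most 57.7% instead of 55.0%. Because the final analysis waits for 184 control events, the main effect is a delay of about 0.6-5.6 months with the 6-year limit, or 0.3-2.9 months without it. These figures assume that every site takes the strict reading, so on those assumptions they are upper ends. The share and the gap are not given in the documents, and a larger share would scale the delay up. The conclusion that the comparison is essentially unaffected rests on individual randomization and on readings that do not differ by arm.

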10.3 Disease-Free Survival

From date of randomization to date of first documentation of relapse/recurrence or death due to any cause. Patients last known to be alive without report of relapse/recurrence are censored at date of last contact.

10.4 Overall Survival

Measured from date of randomization to date of death from any cause. Patients known to be alive are censored at date of last contact.

10.5 Performance Status

Patients will be graded according to the Zubrod Performance Status Scale.

POINT	DESCRIPTION
0	Fully active, able to carry on all pre-disease performance without restriction.
1	Restricted in physically strenuous activity but ambulatory and able to carry out work of a light or sedentary nature, e.g., light housework, office work.
2	Ambulatory and capable of self-care but unable to carry out any work activities; up and about more than 50% of waking hours.
3	Capable of limited self-care, confined to bed or chair more than 50% of waking hours.
4	Completely disabled; cannot carry on any self-care; totally confined to bed or chair.

11.0 STATISTICAL CONSIDERATIONS

11.1 Accrual Goal

We anticipate that 113 eligible patients will be randomized per year to this study on a group-wide basis. We will also assume that 10 percent of enrolled patients will be found to be clinically or pathologically ineligible and hence, not randomized so our Step 1 sample size will be inflated to account for this. Based on an extensive review of the contemporary literature (see [Section 2.0, Table 1](#)), we estimate that 3-year disease free survival (DFS) for patients at increased risk for pelvic and iliac node metastasis undergoing a standard pelvic lymphadenectomy is 55%. A poll of centers of excellence suggest that a 10-12% improvement in 3-year DFS (65-67%) for patients in extended lymphadenectomy would be meaningful and establish extended node dissection as the standard of care in this patient population. Assuming exponential survival, 5 years of patient accrual, 3 additional years of follow-up and a sample size of 564 eligible patients (282 per arm), the study has 85% power to detect a 28% reduction in the hazard rate of progression or death with extended lymph node dissection compared to limited

dissection (hazard ratio 0.72). This corresponds to an improvement in 3-year DFS from 55% to 65% or alternatively median DFS would be extended from 3.5 to 4.8 years if the DFS distributions are exponential. We will use a one sided stratified log rank test with $\alpha = 0.025$, and the analysis will be intent-to-treat.

Assuming an ineligibility rate of 10%, total accrual (eligible + ineligible patients) to the initial step is expected to be 620 patients.

As a secondary endpoint, overall survival is also of great interest. If extended lymph node dissection is found to be statistically significantly better than standard lymph node dissection with respect to DFS, then an analysis of the survival endpoint will follow. We will allow for three more years of follow-up after the primary analysis has been conducted to assess potential survival differences. If we assume that the standard arm has 5-year survival of 55% then we will have 83% statistical power to detect a hazard ratio of 0.72 (55% vs. 65% survival at 5 years) using a one-sided stratified logrank test with alpha=0.025.

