The size of the eligible population is estimated as 340-370 annually from these centers alone before expanding the trial to additional sites. We anticipate a high acceptance to the trial by patients based on experience with similar trial designs in gastric and esophageal cancers. These are data provided by the surgeons at these sites and represent a high-side estimate of annual accrual. There is an obvious large pool of patients for accrual and commitments from each of these centers to accrue. In order to achieve an accrual rate of 13 patients/month when each of these sites has IRB approval we would require approximately one half of the estimated accrual capability from these sites only. Since this survey, we have obtained commitments from BC Cancer Agency ([name]), Cleveland Clinic ([name]), Rochester ([name]), and University of Texas Health Science Center San Antonio ([name] and [name]). These are high volume SWOG sites. ALLIANCE formally reviewed and unanimously approved the trial. This will facilitate participation from MSKCC and adds vanguard sites at University of Chicago ([name] and [name]), Ohio State ([name]), and UCSF ([name]). ECOG-ACRIN has also agreed to participate and sites expressing interest include Vanderbilt ([name], [name], [name]) and UT Southwestern. If we achieve the accrual required to meet the vanguard feasibility portion of the trial, then the trial would be expanded to other interested centers in SWOG, ALLIANCE and ECOG-ACRIN that meet the credentialing requirements.

Inclusion of Women and Minorities:

This study was designed to include women and minorities, but was not designed to measure differences of intervention effects. The anticipated accrual in the ethnicity/race and sex categories is shown in the table below. Both men and women of all races and ethnic groups are eligible for this study.

Ethnic Category	Females	Males	Total
Hispanic or Latino	10	43	53
Not Hispanic or Latino	116	451	567
Total Ethnic	126	494	620
Racial Category			

Ethnic Category	Females	Males	Total
American Indian or Alaskan Native	0	2	2
Asian	2	9	11
Black or African American	14	36	50
Native Hawaiian or other Pacific Islander	0	0	0
White	110	447	557
Racial Category: Total of all Subjects	126	494	620

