If this trial continues past the two feasibility assessments, three formal interim analyses are planned to evaluate the efficacy of extended lymph node dissection. The first will be conducted after 25% of the expected events (relapse or death without relapse) have been reported on the control arm. The second after 50% of the events have occurred on the control arm, and the third when 75% of the expected events have occurred on the control arm. See the [table](#) for number of events and expected time when events will occur. The interim analyses will be conducted based on the number of events in the standard LND arm and not the estimated calendar time. Estimated number of events in the experimental arm are provided for descriptive purposes only. At each interim analysis, evidence suggesting early termination of the trial and a conclusion that the extended lymph node dissection is no better than standard dissection would be if the alternative hypothesis of a 28% improvement in DFS with the experimental arm is

rejected at the 0.005 level, using an extension of the logrank test that allows for testing a relative risk not equal to 1. In addition, the null hypothesis of no difference in DFS will be tested at the one-sided level of 0.005. If the decision is to continue the study for the full specified period, we estimate the final analysis will occur approximately three years after completion of accrual. The final DFS analysis will be conducted when 184 events have been observed on the standard LND arm, using a one-sided stratified logrank test with a significance level of 0.022 to account for multiple interim testing.

If the DFS analysis is statistically significant, the survival analysis will follow approximately two years later when 166 deaths have occurred on the control arm. The stratified logrank test will be performed at the one-sided 0.025 level.

Interim Analysis	Anticipated Analysis Time Relative to Study Activation	Percent of Expected Information On Control Arm	# of Events in the Control Arm (Standard LND)	Anticipated # of Events on Experimental Arm (Extended LND) (assuming the alternative hypothesis)
1	38 months	25%	46	34
2	56 months	50%	92	70
3	73 months	75%	139	108

With 282 eligible patients randomized to each arm, estimates of morbidity and toxicity frequencies can be estimated to within \pm 6% (95% confidence interval).

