Figure 1. Increased neutrophil infiltration and STAT3 activation in the benign lymph nodes of muscle invasive bladder cancer is associated with lessened overall survival. In a cohort of 20 patients with muscle-invasive bladder cancer, survival was compared in cohorts divided by (a) CD15⁺ cell (i.e., neutrophil) count or (b) pSTAT3⁺ cell count above or below the mean within the overall cohort.

A wide spectrum of positive staining was seen for each of the assessed biomarkers. Analyses of overall survival were conducted using the Kaplan-Meier method (with the log-rank test) based on subgroups characterized by high (above the mean) or low (below the mean) biomarker expression. There was a significant extension of overall survival amongst patients with a decreased degree of neutrophilic infiltration ($P<0.01$; Figure 1). Also, lower levels of pSTAT3 were associated with improved overall survival ($P=0.04$; Figure 1). In contrast, no difference in outcome was observed based on VEGFR1 or CD68 expression above or below median values ($P=0.60$ and $P=0.28$, respectively). Also, no difference in survival was observed when segregating patients by clinical stage ($P=0.73$).

2. Statistical Plan

The primary endpoint of the clinical study is to determine whether use of radical cystectomy with extended lymphadenectomy yields an improvement in DFS as compared to radical cystectomy with standard lymphadenectomy. The study uses a historical estimate of 55% 3-year DFS in association with standard lymphadenectomy, and suggests that a 10-12% improvement (i.e., to 65-67%) would be meaningful and

establish extended lymphadenectomy as a stand of care. With these estimates in mind, assuming exponential survival, 5 years of patient accrual, 3 additional years of follow-up and a sample size of 564 eligible patients (282 per arm), the study has 85% power to detect a 28% reduction in the hazard rate of progression or death with extended lymphadenectomy (hazard ratio, 0.72). Assuming an ineligibility rate of 10%, total accrual is estimated to be approximately 620 patients.

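### The expected 620 Step 1 registrations do not match the stated 10% exclusion: 564 randomized patients need about 627

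*Combined protocol and SAP*

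**What the plan says.** Section 11.1 (Accrual Goal) gives the exclusion assumption with its base: "10 percent of enrolled patients will be found to be clinically or pathologically ineligible and hence, not randomized so our Step 1 sample size will". The sentence closes by saying that the Step 1 number is raised to allow for the loss. The power statement in the same section rests on "a sample size of 564 eligible patients (282 per arm"). The accrual forecast agrees with that target: "We anticipate that 113 eligible patients will be randomized per year to this study on a group-wide basis", and accrual is planned over 5 years. The section then gives the inflated figure: "Assuming an ineligibility rate of 10%, total accrual (eligible + ineligible patients) to the initial step is expected to be 620 patients".

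The same total appears in two other places. Section 18.2, in the statistical plan for the pre-metastatic niche study, says: "Assuming an ineligibility rate of 10%, total accrual is estimated to be approximately 620 patients". The planned-enrolment table under Inclusion of Women and Minorities in Section 2.0 closes with "Racial Category: Total of all Subjects 126 494 620".

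Section 11.2 works from the randomized number per arm and not from registrations. On precision it says "With 282 eligible patients randomized to each arm, estimates of morbidity and toxicity frequencies can be estimated to within" ±6%, and on timing "The final DFS analysis will be conducted when 184 events have been observed on the standard LND arm".

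**The concern.** When a loss rate is a share of the patients who enter, the number that must enter is the target divided by one minus the rate. Section 11.1 fixes this base twice. The 10% is of enrolled patients, and the 620 is the total of eligible and ineligible patients at the first step. Multiplying the target by 1.10 is a different calculation, because it takes 10% of the patients who remain. The result is too small for the stated rate.

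At stake is whether the Accrual Goal section agrees with itself. Under its own assumption, the registration figure is not expected to deliver the randomized number on which the power is based.

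**Working it through.** **Inputs**

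- Randomized target: 564, or 282 per arm (Section 11.1; Section 11.2 gives 282 per arm).
- Exclusion: 10% of Step 1 patients, not randomized (Section 11.1).
- Stated Step 1 total: 620 (Sections 11.1 and 18.2, and the table in Section 2.0).
- Design: 3-year DFS 55% on control, hazard ratio 0.72, exponential DFS, 5 years of accrual plus 3 of follow-up, one-sided 0.025 (Section 11.1). The final test level is 0.022 and the trigger is 184 control-arm events (Section 11.2).

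**Step 1. Reproduce the plan's figure.** 564 x 1.10 = 620.4, which rounds to 620.

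**Step 2. Apply the rate to its stated base.** Registrations = randomized/(1 − rate) = 564/0.90 = 626.7, about 627. The gap is 7 registrations, and 7/627 = 1.1%.

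**Step 3. Read 620 backwards.** 620 x 0.90 = 558 randomized, 6 fewer than 564. The rate that 620 implies is (620 − 564)/620 = 56/620 = 9.0%.

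**Step 4. Confirm that 564 is the firm number.** 113 per year x 5 years = 565. The control hazard is −ln(0.55)/3 = 0.199 per year. With uniform accrual over A = 5 years and F = 3 further years, the probability of an event is 1 − [exp(−λF) − exp(−λ(A+F))]/(λA). With 282 per arm this gives 183.8 control events and 151.1 on the extended arm, 335.0 in total. Schoenfeld power is Φ(√(335.0/4) x |ln 0.72| − 1.96) = 85.2%. These results match the stated 184 events and 85%, so the design rests on 564.

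**Step 5. Size the effect if registration stopped at exactly 620 and 10% were excluded (279 per arm).**

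| Quantity | 282 per arm | 279 per arm |
|---|---|---|
| Total events at a fixed 8 years | 335.0 | 331.4 |
| Power at 8 years, one-sided 0.025 | 85.2% | 84.9% |
| Power at 8 years, one-sided 0.022 | 83.9% | 83.5% |
| Months to 184 control events (60-month accrual) | 96.1 | 97.3 |
| Total events at 184 control events | 335.3 | 335.6 |
| Power at 184 control events, one-sided 0.025 | 85.3% | 85.3% |
| Largest 95% half-width, 1.96 x √(0.25/n) | 5.84% | 5.87% |

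If the 558 patients accrue at 113 per year (59.3 months), 184 control events come at 96.9 months. The delay is therefore about 0.8 to 1.2 months.

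**Step 6. Compare with chance variation.** The standard deviation of the number randomized from 620 at 90% is √(620 x 0.90 x 0.10) = 7.5, which is more than the shortfall of 6.

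**The case against.** The strongest reply is that nothing depends on 620. Section 11.1 calls it an expected figure, Section 18.2 calls it approximate, and no passage says that registration stops there. If 10% were excluded, the natural course would be a few more registrations until 564 were randomized. The 10% is itself a round planning value: one point either way moves the randomized number by 6.2, as much as the whole discrepancy. The document is also stamped closed as of April 2017. If that means closed to accrual, the correction has no operational effect. All of this stands, and it limits the point to a minor one.

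It does not remove the inconsistency. Rounding does not explain it, because 626.7 rounds to 627 or 630, whereas 564 x 1.10 gives 620 almost exactly. The cause is the base of the percentage.

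A reader might infer that the trial is underpowered or was planned to randomize only 558. The documents do not support this. Power is stated for 564, the final analysis waits for 184 control-arm events, and 558 arises only if registration ends at exactly 620.

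A reader might also infer that 9% was the intended rate, since 620 x 0.91 = 564.2. Nothing in the documents supports 9%. Sections 11.1 and 18.2 both say 10%, and adopting 9% would fit the assumption to the output of the wrong formula.

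**Conclusion.** The inconsistency is real and small. Under the plan's own definition, the Step 1 projection should be about 627; the stated 620 is 7 registrations (1.1%) low and is expected to give 6 fewer randomized patients than the design uses. The conclusion on the arithmetic needs only that the 10% be a share of enrolled patients, which Section 11.1 says.

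The sizes given for power and timing assume exponential DFS, uniform accrual, no loss to follow-up and Schoenfeld's approximation. They also assume the unfavourable case in which registration stops at 620. Even then the loss is 0.3 to 0.4 percentage points of power at a fixed calendar time, or about one month's delay if the analysis waits for its events. Precision stays within ±6%.

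**What to change.** Keep the 10% assumption. Restate the expected Step 1 accrual as about 627 in Section 11.1 and in the statistical plan of Section 18.2. Update the planned-enrolment table in Section 2.0 to the same total. Its totals are sums of cells (126 + 494 by sex; 53 + 567 by ethnicity; 2 + 11 + 50 + 557 by race), so 7 patients have to be spread over those cells.

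The cost is one figure in each of two sections and a small adjustment to one table of anticipated accrual. The 564 randomized patients, 282 per arm, the 184-event trigger, the stated 85% power, the ±6% precision and the analyses stay as they are.
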